saliva accumulates but rather allow it to accumulate in the mouth and then drain gently into the cup. The time will be noted by the investigator and, after 15 minutes, the investigator will advise the subject that the test has ended. The investigator will again weigh the cup and saliva and record the weight. One gram will be understood to be approximately equivalent to 1 mL of saliva and the new weight recorded. The weight per minute will be calculated and understood to be the subject's current unstimulated whole saliva flow rate (UWSFR). If the rate is < 0.2 mL/min the subject will be advised that the inclusion criteria for the remainder of the study have been met and that the study will continue. This level was selected as a "cut-off" both because it is the level at which existing literature recognizes genuine mouth dryness to likely exist and also because of our belief that subjects who perceive dryness in the presence of relatively 'normal' salivary flow rates, may be unreliable in their reports of beneficial effects of study agents. Subjects who do not meet the inclusion criteria will be given \$25 in appreciation for their participation to this time and then dismissed.

6. First Test agent.

The subject will then be seated in a quiet dimly lit room and asked to refrain from speaking, including using phones, unless it is essential (e.g. they are feeling badly enough that their participation needs to be paused or stopped). After not less than one (1) minute a visual analog scale (VAS) of dryness will be recorded in response to the question, "How much discomfort are you feeling from your dry mouth?". (See Appendix 9). They will then be administered, by the investigator, a dose of 3 sprays (to the anterior dorsal of the tongue) of the randomly selected experimental or alternative agent with instructions to "spread it around in your mouth." An electronic timer will be started by the investigator at that time. The investigator will be administering the agents after priming the spray bottle twice before aiming the first spray to the anterior dorsal of the subject's tongue. Neither the investigator nor the subject will know the identity of the administered agent.

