3. Administration of second test agent (which ever was not used in Session 1). Recordings of VAS regarding the feeling of dryness will be made just before and after administration of the test agent and then every 15 minutes in a manner identical to that of Session 1. Subjects will be instructed to stop the timer when they feel the effect of the test agent has dissipated completely; this will mark the endpoint of the duration of effect, which will be recorded.
4. Survey of experience with second test agent.

This will utilize the same survey form used in Session 1 (Appendix 11).

At this point, the subject has completed the required commitment to the study, and will be de-briefed, including being requested to verbally supply any comments they feel might be useful in future studies in which they might participate. Subjects will be offered additional

information and/or referrals to a dry mouth clinic as needed. They will be compensated \$50 plus parking for their participation and dismissed.

(See also Appendices 4 and 5 for flow chart and schedule of activities.)

5.1.2. Amount of agent to be tested. And 5.1.3. Investigational drug/device.

The manufacturer of Biotène Moisturizing Mouth Spray has directions (Appendix 12) printed on the spray bottle stating, “Spray directly into the mouth, onto the tongue, and spread thoroughly inside the mouth. Use as required. Safe to swallow when used as directed.” In an effort to minimize variation in the amount dispensed for this study but to remain essentially consistent with the manufacturer’s directions the investigator will assume the following calibration protocol for each subject:

1. Weigh the empty cup to be used for collection of whole saliva.
2. Prime the spray bottle by squeezing firmly at least twice, toward a sink or bucket. This “spray sample” will then be discarded.
3. Using the identical technique, three sprays will then be collected in a second empty cup and weighed. This will serve as a “calibration sample.” This sample will then be discarded but the empty cup retained.
4. The investigator will then direct three sprays to the anterior dorsal of the tongue. Utilizing a total of three sprays is intended to mimic what a xerostomic patient likely would do. Having the investigator, instead of the subject, administer the agent is expected to make the amount of agent expressed be generally uniform among subjects.

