5. The same cup will be handed to the subject and will be used for collection of the sample of whole saliva over a period of 15 minutes.

The organization and administration of the test agents will be completed in the laboratory of [name], Pharm D, Manager of Investigational Drug Services (IDS) here at the University. Each bottle of test agent (either Biotène Dry Mouth Moisturizing Spray or sterile water) will be appear in identical spray bottles. The possibility exists that the investigator or subject may notice the scent and viscosity differences between the different agents, however this will unlikely impact the outcome measures. To assess the impact of these differences, the post-test questionnaire (Appendix 11) will ask subjects if they think they received the moisturizing spray or the alternative (sterile water). The spray bottles will be unlabelled except for a unique number which identifies the contents to IDS laboratory and the statistician. The true identities of the bottles will be unknown to the investigator and the subjects. The contents of the test agent will be linked to each subject through a randomization process completed by IDS.

A recent study (Jose et al, 2016) sponsored by the manufacturer (GlaxoSmithKine) of Biotène spray investigated the comparative effect of 3 of its products with 2 hours as the primary endpoint. Since xerostomia lasting longer than 2 hours may be uncomfortable, demonstrating that an agent provides relief close to this time frame would have potential therapeutic and commercial value. Although the study design was different, 49.5% of subjects reported that the spray was good, very good, or excellent at “relieving the discomfort of dry mouth” 2 hours after use of the spray. A previous study (Shahdad et al. 2005) also discovered that most subjects achieved relief utilizing topical agents after 2 hours. In this study involving a Biotène gel, it was found that the viscosity is positively correlated to the retention time of the agent (Shahdad et al. 2005). Therefore, we expect the less viscous experimental spray to have a shorter retention time than the expected 2 hours. Therefore, 2 hours will be defined as the maximal endpoint in this study. We expect that the crossover design and qualitative measures will aid health care providers and patients to derive benefit from Biotène Moisturizing Mouth Spray or water.

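### Section 5.1.2 numbers the 15-minute saliva collection after the dose, contradicting section 5.1.1 and Appendix 6

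*Combined protocol and SAP*

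**What the plan says.** Section 5.1.2 (run together with 5.1.3) sets out a calibration procedure for each subject. Its stated aim is "In an effort to minimize variation in the amount dispensed for this study". The steps, in order, are:

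1. Weigh the empty cup that will be used for saliva.
2. Prime the bottle and discard the spray.
3. Collect and weigh a three-spray calibration sample in a second cup; then "This sample will then be discarded but the empty cup retained".
4. Dose: "The investigator will then direct three sprays to the anterior dorsal of the tongue".
5. Collect saliva for 15 minutes: "The same cup will be handed to the subject and will be used for collection of the sample of whole saliva".

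Section 5.1.1 gives the opposite order. At Visit 1, flow rate is item 4 and the agent is item 5. At Visit 2, flow rate is item 2 and the agent is item 3. The detailed descriptions in 5.1.1 agree: the flow rate is measured first, the subject then sits quietly for at least a minute, a pre-dose discomfort score is taken, and only then is the dose given and the timer started. The Appendix 6 schedule lists sialometry above Test 1 and Test 2.

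**The concern.** Two current procedural texts give opposite orders for the same two acts, and the one in 5.1.2 would damage the measurements if it were followed.

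The main outcome is the time from dosing until the subject feels that the effect has gone. The saliva test tells the subject to stop swallowing and to let saliva gather, "allow it to accumulate in the mouth and then drain gently into the cup". Doing this straight after the dose removes agent from the mouth while the duration timer runs.

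The flow rate is meant to be unstimulated. Section 2.1 describes the product's flavorings as salivary stimulants, so a rate taken after the product is not unstimulated. After either agent, whatever drains into the cup is weighed as saliva. Section 5.1.1 uses the mean of the two visits' flow rates when comparing flow with duration of action, so an error in either rate enters that comparison.

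Step 5 also does not say plainly which of the two cups it means.

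**Working it through.** The plan has no figure of its own to reproduce here. The check is one of order, followed by simple arithmetic on what the wrong order would do.

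**Order of collection and dose**
- 5.1.1 Visit 1 list: collection (item 4), then agent (item 5).
- 5.1.1 Visit 2 list: collection (item 2), then agent (item 3).
- 5.1.1 detailed descriptions: collection, then rest and pre-dose score, then agent.
- Appendix 6: sialometry is listed above the tests.
- 5.1.2: agent (step 4), then collection (step 5).

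Only 5.1.2 differs.

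**Inputs**
- Dose D = 0.5 mL (2.3; given as approximate in 8.2).
- Collection time T = 15 minutes (5.1.1 and 5.1.2).
- Entry limit 0.2 mL/min (3.2).
- Maximum observation 2 hours (5.1.1).
- 1 g taken as 1 mL. The protocol says this for saliva; applying it to the agents is an assumption.
- Fraction f of the dose that drains into the cup: not in the documents, so shown as a range.

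**Volume leaving the mouth in the first 15 minutes** = flow rate × T
- At 0.20 mL/min: 0.20 × 15 = 3.0 mL, and 3.0/0.5 = 6 times the dose.
- At 0.05 mL/min (an illustrative low rate): 0.05 × 15 = 0.75 mL, and 0.75/0.5 = 1.5 times the dose.

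The window is 15/120 = 12.5% of the maximum observation time. The discomfort scores at 1 and 15 minutes fall within it or at its end.

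**Rise in the recorded flow rate** = f × D / T
- f = 0.10: 0.05/15 = 0.003 mL/min, 1.7% of the 0.2 limit.
- f = 0.25: 0.125/15 = 0.008 mL/min, 4.2%.
- f = 0.50: 0.25/15 = 0.017 mL/min, 8.3%.
- f = 1.00: 0.5/15 = 0.033 mL/min, 16.7%.

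Any flow stimulated by the product would add to these figures.

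**Effect on the two-visit mean**, if only the Visit 2 rate is taken after dosing: half the rise.
- f = 0.50: 0.25/30 = 0.008 mL/min.
- f = 1.00: 0.5/30 = 0.017 mL/min.

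For a true rate of 0.05 mL/min, the mean would be too high by 0.0083/0.05 = 17% to 0.0167/0.05 = 33%. For a true rate of 0.20 mL/min it would be too high by 4% to 8%. The relative error is largest in the driest subjects.

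**Which visit is exposed**
- Sections 4.1 and 8.3 allocate subjects as they qualify, and 5.1.1 ends participation after the Visit 1 flow test if the limit is not met. The qualifying rate must therefore exist before any agent is assigned. A collection after dosing at Visit 1 could only be an additional one; it would still drain the dose.
- At Visit 2 subjects continue whatever their flow rate, so no such check would stop the 5.1.2 order from being used.

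**The case against.** The strongest reply is that the intended order is not in doubt. Section 5.1.1 states it in its lists for both visits and again in its detailed text, and Appendix 6 agrees. Section 5.1.2 is about the amount of agent and is not a visit schedule, so step 5 is probably a slip in drafting. This is fair, and it is why the point is minor. It does not remove the conflict, because 5.1.2 is a numbered list that the investigator is told to use for each subject.

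On the cup, step 1 names the saliva cup and step 3 calls the other a second cup, so a careful reader can work out which is meant. That stands; the wording is loose rather than wrong.

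Two stronger readings are tempting, and the documents do not support them.

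- A reader might infer that subjects just under the limit would be wrongly excluded at Visit 1 because agent is weighed as saliva. Allocation follows qualification (4.1, 8.3) and the flow test ends participation before dosing (5.1.1), so the rest of the protocol closes that path. At Visit 2 the flow rate excludes no one.
- A reader might infer that the calibration weight in step 3 is itself an error, since 5.1.2 sets no acceptable range and does not say to record it, and the protocol grants that "the investigator or subject may notice the scent and viscosity differences between the different agents". But no difference in volume and no bias in duration is shown. Three sprays against three sprays is a legitimate contrast, and the dose is standardised by priming and by having the investigator give it. Recording the weight would be useful documentation; its absence is not a mistake in the plan.

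**Conclusion.** The point holds as a minor internal contradiction with a real consequence if the wrong text is followed. Step 5 of 5.1.2 is out of order. Followed as numbered, it drains agent from the mouth during the first 15 minutes of the duration measurement and yields a flow rate that is not unstimulated. With half to all of the dose draining out, the recorded rate rises by 0.017 to 0.033 mL/min, and the two-visit mean by 0.008 to 0.017 mL/min if only Visit 2 is affected.

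These sizes rest on the assumed fraction drained, on 1 g = 1 mL for the agents, and on no added stimulation. The effect on measured duration cannot be sized from the documents, nor can it be said whether the two agents would be affected equally. Nothing in the documents shows that any subject was tested in the 5.1.2 order.

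**What to change.** In 5.1.2, move step 5 to directly after step 1, before priming, calibration and dosing, and renumber. At the start of the moved step, name the cup weighed in step 1 and state that it is used for saliva only. The list then agrees with 5.1.1 and Appendix 6.

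The cost is a wording change to one list; no procedure, visit length or masking arrangement changes. Appendix 13 shows that some subjects had already taken part, so it is worth confirming from the source records that their saliva was collected before dosing.

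Optional: record the net weight of the calibration sample at each visit. The weighing is already planned, so this adds one number per visit. It is a documentation suggestion, not a correction.

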5.2. Efficacy Assessment

This pilot study was developed because estimated data regarding the duration of action of a single dose of Biotène Moisturizing Mouth Spray is not available. The estimated duration is necessary for calculating the sample size for a definitive study. At the completion of the pilot, the mean duration of action of both the experimental and control agents will be forwarded to the biostatistician ([name]) for calculation of the sample size for the definitive study. When the required sample size is returned to investigators, plans for the definitive efficacy assessment will be developed.

5.3 Safety Assessments

During subject identification and recruitment comprehensive medical histories of potential subjects will be gathered. Persons whose histories suggest they are rated ASA III or higher will not be accepted in the study. At the beginning of each visit subjects’ medical histories will be updated and their vital signs (blood pressure, pulse, respiration rate, presence and level of pain) will be recorded by the investigator. If the investigator, who is a dentist, feels that the subject would not be a safe candidate for a routine dental procedure that day, s/he will be re-scheduled to another day or discharged from the study.

5.4. Assessment of Subject Compliance

Subjects will be under the direct supervision of the investigator during the observation period for up to 3 hours.

5.5 Data and Speciman Banking for Future Research Use

N/A

5.6 Genetic/Genomic Research Activities

N/A

5.7 Costs to the Subject

There are no costs for subjects nor for potential subjects.

5.8 Payment for Participation

Potential subjects who are screened for the study will be compensated for parking in the ramp garage plus \$25 for their first session. Eligible subjects who return and complete the second session will be compensated for their parking plus an additional \$50.

5.9 Return of Individual Research Results

In their second session subjects will be offered the results of their sialometry flow test and an interpretation by the investigator. At their request, patients who have concerns about their test results will be given additional general information about managing their condition and also encouraged to see their own dentist or the EIOH Oral Medicine Clinic for further evaluation.

6. CONCOMITANT AND DISALLOWED MEDICATIONS

Subjects may take normal daily medications as usual.

7. SUBJECT WITHDRAWALS

Eligible subjects will be enrolled into the study on a rolling basis until a minimum number of subjects is attained. If the withdrawal of a subject causes an insufficient number of subjects to be enrolled, the recruitment of another subject will be undertaken.

8. STUDY DRUG/DEVICE/BIOLOGIC ADMINISTRATION/ASSIGNMENT

Note: The side of the box with the device information is included in Section 50 of the RSRB application.

8.1. Biotène Dry Mouth Moisturizing Spray

Biotène Dry Mouth Moisturizing Spray (Appendix 12) contains water, polyglycol, propylene glycol, sunflower oil, xylitol, milk protein extract, potassium sorbate, acesulfame

K, potassium thiocyanate, lysozyme, lactoferrin, lactoperoxidase (45 mL). No maximum dosage or interval for usage is specified. Product is to be used *ad libitum*. The Investigational Drug Lab at the University of Rochester Strong Hospital, [name] will be supplying, packaging, and labeling the product as well as the placebo which will consist of distilled water.

The agent of interest is IND/IDE exempt for this clinical investigation as the product is lawfully marketed in the United States for the treatment of symptoms of dry mouth [FDA 21 CFR 312.2(b)/FDA 21 CFR 812.2(c)].

8.2.Dosage of Study Drug/Biologic

For the purpose of this study, 3 streams of the product (approximately 0.5 mL) administered by the investigator will be considered a dose. For consistent dosing, two sprays to prime the spray nozzle will be completed prior to administering a dose to the subject.

8.3.Subject Enrollment/Randomization

Subjects will be allocated to group A or group B using block randomization (Appendix 6). Subjects will be allocated to a group as they qualify for the study. The subject and the investigator will be blinded to the group a subject is allocated to. The products will be labeled identically except for a serial code on the bottle will correspond to the treatment or control. The true identity of the products will be known only to the supplier (the Investigational Drug Lab, University of Rochester Strong Memorial Hospital), and unknown to the investigator and subjects until the completion of the study.

8.4.Accountability of Investigational Supplies

The Investigational Drug Lab of the University of Rochester Strong Memorial Hospital, [name] will be responsible for the formulation and labeling of investigational supplies. The Investigational Drug Lab will be the unblinded third party. The investigator will handle the receipt, storage, dispensing, collection, accountability log, and disposal of the investigational supplies.

8.5.Subject Withdrawal of Study Drug

The agents under investigation have short-lasting and reversible effects that do not require the subject to be monitored following the study period. Subjects may choose to withdraw from the study at any time without consequence and without side effects. The effect of the agents under investigation can be reversed by rinsing out the mouth with warm water.

8.6.Emergency Drug Disclosure

Drug disclosure will be maintained electronically and in envelopes by the Investigational Drug Lab. Drug disclosure should be accessed only in the case of a medical emergency. If

such action is necessary, the Investigational Drug Lab will provide the identity of the administered agent to the investigator and the appropriate medical team will be called. Once the identity of the administered agent is revealed, the subject will be withdrawn from the entire study.

9. SAFETY AND REPORTABLE EVENTS

9.1. Adverse Event Definition

An adverse event is any symptom, sign, illness, or experience which develops or worsens during the course of the study, whether or not the event is considered related to study drug.

9.2. Serious Adverse Event

A serious adverse event is defined as any adverse medical experience that results in any of the following outcomes:

- death;
- is life-threatening;
- requires inpatient hospitalization or prolongation of existing hospitalization;
- results in persistent or significant disability/incapacity;
- is a congenital anomaly/birth defect; or
- requires medical or surgical intervention to prevent permanent impairment or damage.

9.3. Recording Adverse Events

At each subject visit the site study staff will assess adverse events by recording all voluntary complaints of the subject and by assessment of clinical and laboratory features. After the study visit, the subject should be questioned directly regarding the occurrence of any adverse experience during his/her visit.

All adverse events, whether observed by the investigator, elicited from or volunteered by the subject, will be documented. Each adverse event will include a brief description of the experience, the date of onset, the date of resolution, the duration and type of experience, the severity, the relationship to investigational product (i.e., agent or control), contributing factors, and any action taken with respect to the study agent.

The timeframe that recording of adverse events will occur once the subject signs consent until subject completes the study or withdraws from participation. Follow up will occur until the adverse effect has resolved. Follow up of adverse experiences after the subject concludes study participation should be with the investigator, who may decide to refer the subject to a primary care physician.

9.4. Responsibilities for Reporting Serious Adverse Events

The Investigator will record all serious adverse experiences that occur during the study period in the appropriate source documents and/or adverse event (AE) log as applicable. The study period for reporting serious adverse events is from the time of signing consent to the end of the study participation. The principal investigator and appropriate medical response teams will be notified immediately. The Investigator will comply with regulations and RSRB policy regarding the reporting of adverse events.

10. RISK/BENEFIT ASSESSMENT

10.1. Potential Risks

As with all studies, there is a risk of breach of confidentiality. Subjects may be exposed to substances that may elicit an allergic reaction. Also, subjects may undergo temporary oral discomfort while their usual methods of moistening their mouths are forgone.

10.2. Protection Against Risks

The study design minimizes risk by administering a single dose of the agents being tested. The subjects in the study will be under constant surveillance by the investigator. The investigator has a Basic Life Support Training. Follow up of subjects who experience an adverse effect will be followed up by the investigator at no charge, otherwise referred to a primary care physician at the subject's expense.

